11.4 Summary Definition of objective response for patients with B-CLL

	CCR ¹	CR ²	CR ³	nPR ⁴	PR ⁵	PD ⁶
PHYSICAL EXAMINATION						
Nodes ⁷	None	None	None	None	<50%	>50% increase, new nodes
Liver/spleen ⁸	Not palpable	Not palpable	Not palpable	Not palpable	<50%	>50% increase, newly palpable
Symptoms	None	None	None	None	N/A	N/A
PERIPHERAL BLOOD						
ANC	>1500/ μ L	>1500/ μ L	See footnote 3	>1500/ μ L or >50% improvement from baseline	>1500/ μ L or >50% improvement from baseline	See footnote 6
Platelets	>100,000/ μ L	>100,000/ μ L	See footnote 3	>100,000/ μ L or >50% improvement from baseline	>100,000/ μ L or >50% improvement from baseline	See footnote 6
Hemoglobin	>11.0 g/dL without transfusion	>11.0 g/dL without transfusion	See footnote 3	>11.0 g/dL or >50% improvement from baseline without transfusion	>11.0 g/dL or >50% improvement from baseline without transfusion	See footnote 6
Lymphocytes	<4000/ μ L	<4000/ μ L	<4000/ μ L	<4000/ μ L	≥50% decrease	>50% increase to at least 5,000/ μ L
BONE MARROW	N/A	Normocellular ³ ; <30% lymphocytes; no nodules	<30% lymphocytes; no nodules	<30% lymphocytes; bone marrow nodules ⁴	N/A	N/A

1. Clinical complete response (CCR) requires fulfillment of all physical exam and peripheral blood criteria as noted in the table above. No bone marrow biopsy is required to call a patient a CCR; however, patients should have a bone marrow analysis performed within two month of the formal response evaluation where clinical and laboratory evidence of complete response was first seen as instructed in the test schedule to confirm CR as per standard guidelines by the IWCLL.
2. Complete response (CR) requires fulfillment of all physical exam and peripheral blood criteria for a duration of ≥2 months. A bone marrow aspirate and biopsy are required to document the response as a complete within two month of the formal response

evaluation where clinical and laboratory evidence of complete response was first seen (see Section 11.21).

3. Patients who fulfill all criteria for a CR but who have a persistent anemia, thrombocytopenia, or neutropenia related to drug toxicity rather than residual CLL or have hypocellular marrow will be classified as CR with incomplete marrow recovery(CRi).
4. Nodular partial response (nPR) is essentially a patient who appeared to have a CR but nodules were present in the bone marrow. It requires fulfillment of all physical exam and lymphocyte criteria for CR; however, when the bone marrow is done to confirm CR, nodules of malignant lymphocytes are found. Patients must fulfill one or more of the blood count parameters (ANC, Platelets, Hemoglobin) but are not required to meet all 3 of these conditions. See Section 11.215 regarding the distinction between clonal and regenerative nodules.
5. Partial response (PR) requires fulfillment of at least two of the above-noted decrease in circulating lymphocytes, regression in adenopathy and regression in hepatosplenomegaly, and at least one other parameter listed above for a duration of ≥ 2 months. See Section 11.22.
6. Progression: Fulfilling the criteria as noted in section 11.23. Prior to the formal response evaluation, baseline on study measurements will be used to determine disease progression (e.g. not cycle by cycle comparisons). Once patients undergo formal response evaluation, the nadir value at either baseline or time of response will be used for evaluating future disease progression. In the absence of other indices of clinical progression, the presence of a ≥ 2 g/dL decrease in hemoglobin or a $\geq 50\%$ decrease in platelet count and/or absolute neutrophil count will not exclude a patient from continuing on the study. Although not mandatory, bone marrow aspirate and biopsy are strongly encouraged to better define the cause of the suppressed counts (e.g., treatment versus disease-related).
7. Measurement of lymphadenopathy will be determined on physical exam by adding the sum of the products of the maximal perpendicular diameters of measured lesion(s). No simultaneous increase in the size of any lesions or the appearance of any new lesions may occur for 2 consecutive evaluations at least 1 month apart. Minor fluctuations are acceptable as long as they don't exceed 50% of previous measurement. However, if they do exceed 50% of the previous measurement, treatment should be held for 2 consecutive cycles to rule out the possibility of nodes that wax and wane. For purposes of determining CCR and nPR, all nodes on physical exam need to be ≤ 1.5 cm in maximal dimension or documented to be free of CLL by biopsy. NOTE: Information from CT scans regarding lymphadenopathy is not considered in the standard classification of response with the exception of the patients fitting criteria of section 11.218 and 11.227.
8. Measurement of hepatosplenomegaly will be determined by noting the maximal distance below the respective costal margins of palpable hepatosplenomegaly during rest (e.g., not during deep inspiration). NOTE: Information from CT scans regarding hepatosplenomegaly is not considered in the standard classification of response with the exception of the patients fitting criteria of section 11.218 and 11.227.

12.0 Descriptive Factors

- 12.1 Rai Stage: 0 vs. 1 vs. 2 vs. 3 vs. 4. (Appendix II)
- 12.2 CD38⁺ expression: Positive ($\geq 30\%$) vs. negative ($< 30\%$).
- 12.3 Chromosomal anomalies as detected by FISH: 13q- vs. 12+ vs. 11q- vs. 17p- vs. other abnormality vs. negative FISH.
- 12.4 IgVH mutation status: Mutated ($\geq 2\%$) vs. unmutated ($< 2\%$) vs. indeterminate.
- 12.5 ZAP-70 expression: Positive ($\geq 20\%$) vs. negative ($< 20\%$).

13.0 Treatment/Follow-up Decision at Evaluation of Patient

13.1 Continuation of treatment

Patients who are CCR, CR, CRi, nPR, PR, or SD will continue treatment per protocol.

13.2 Progressive disease (PD)

If the patient develops PD at any time during active treatment they will complete an end of treatment visit 3-4 weeks from the last dose of treatment. The patient will then go to survival follow-up. Patients will then be followed in survival follow-up per Section 4.2.

13.3 If the patient develops unacceptable adverse events, if the treating physician feels it is in the patient's best interest, or if the patient refuses treatment, study treatment will be discontinued and the patient will complete an end of treatment visit 3-4 weeks from the last dose of treatment. The patient will then go directly to survival follow-up. Patients will then be followed in survival follow-up per Section 4.2.

13.4 Duration of therapy

Patient will be treated as indicated in section 7.0, unless they have progressive disease or unacceptable toxicity or withdrawal. Patients who discontinue treatment will complete an end of treatment visit and continue to survival follow-up.

13.5 Ineligible

A patient is deemed ineligible if after registration, it is determined that at the time of registration, the patient did not satisfy each and every eligibility criteria for study entry.

- If the patient received treatment, all data up until the point of confirmation of ineligibility must be submitted. Survival follow-up will be required per Section 4.2.
- If the patient never received treatment, on-study material and the End of Active Treatment/Cancel Notification Form must be submitted. No further data submission is necessary.

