13.7 Major Violation

A patient is deemed a major violation, if protocol requirements regarding treatment in cycle 1 of the initial therapy are severely violated that evaluability for primary end point is questionable. If the patient received treatment, the patient may continue treatment at the discretion of the physician as long as there are not safety concerns. The patient will continue in the Active Monitoring/Treatment phase of the study, as per section 4.0 of the protocol.

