16.0 Statistical Considerations and Methodology

16.1 Overview:

This is a Phase II study designed to assess the overall response rate of daratumumab and ibrutinib for relapsed/refractory CLL in two groups independently: Previously received Ibrutinib (Cohort 1) and Ibrutinib naïve (Cohort 2).

16.11 Primary Endpoint:

The primary endpoint in each cohort is the overall response rate after 6 cycles of treatment with daratumumab in combination with ibrutinib (end of Cycle 7). All patients meeting the eligibility criteria who have signed a consent form and have begun treatment will be evaluable for overall response, with the exception of patients who are determined to be a major treatment schedule violation.

16.12 Sample Size:

The phase II study design to be used in each group is fully described in section 16.2. A maximum of 22 evaluable Cohort 1 and 26 evaluable Cohort 2 patients will be accrued unless undue toxicity is encountered. We anticipate accruing an additional 4 patients (2 Cohort 1, 2 Cohort 2) to account for ineligibility, cancellation, major treatment violation, or other reasons. Maximum projected accrual is 52 patients overall.

16.13 Accrual Rate and Study Duration:

The anticipated accrual rate is approximately 2-3 patients per month. Therefore, the accrual period for this phase II study is expected to be about 2 years. The maximum total study duration is expected to be approximately 7 years, or until the last patient accrued has been observed for at least 5 years. The earliest date anticipated for presentation of results is at approximately 2.5 years, or when the last patient accrued has completed the cycle 7 response assessment.

16.2 Statistical Design:

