16.21 Decision Rule for previously received Ibrutinib group (Cohort 1)

Since patients in this group have been previously treated with Ibrutinib, the patients may have a plateaued response to ibrutinib. A response rate of at least 20% with the addition of daratumumab to ibrutinib would be of interest.

The largest success proportion where the proposed treatment regimen would be considered ineffective in this population is 5%, representing a response by chance alone. The smallest success proportion that would warrant subsequent studies with the proposed regimen in this patient population is 20%. The following one-stage binomial design uses 22 evaluable patients to test the null hypothesis that the true success proportion in a given patient population is at most 5%.

16.211 Final Decision Rule

Enter 22 evaluable patients into the study. If 2 or fewer successes are observed in the first 22 evaluable patients, we will consider this regimen ineffective in this patient population and terminate this study. Otherwise, if the number of successes is at least 3, this will be considered evidence of promising activity and the treatment may be recommended for further testing in subsequent studies.

16.212 Power and Significance Level

Assuming that the number of responses is binomially distributed, with a significance level of 9%, the probability of declaring that the regimen warrants further studies (i.e., statistical power) can be tabulated as a function of the true success proportion as shown in the table below.

If the true success proportion is...	0.05	0.10	0.15	0.20
Then the probability of declaring that the regimen is promising and warrants further study is...	0.09	0.38	0.66	0.85

16.22 Decision Rule for Ibrutinib naïve group (Cohort 2):

In a previous study including 85 patients with relapsed/refractory CLL treated with single agent ibrutinib, the overall response rate at 8 months was 54%. The overall response rate was the same regardless of dose level received (51 patients received 420 mg and 34 received 840 mg). An increase in overall response rate after 8 months of treatment with the combination of daratumumab and 420 mg of ibrutinib would be of interest.

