16.322 The MRD response rate at any time during the course of treatment with daratumumab plus ibrutinib will be estimated by the number of patients who achieve MRD negative response in both blood and bone marrow at any time during combination treatment divided by the total number of evaluable patients. Exact binomial 95% confidence intervals for the true success rate will be calculated. In patients who achieve MRD negative response, time to achieve MRD negative response will be summarized descriptively (median, range). Time to achieve MRD negative response is defined as time from registration to the earliest date of documentation of MRD negative response in both blood and bone marrow.

16.323 Progression-free survival is defined as the time from registration to the earliest date of documentation of disease progression or death due to any cause. Patients who receive subsequent treatment for CLL before disease progression will be censored on the date of their last disease assessment prior to initiation of the subsequent treatment. The distribution of progression-free survival will be

estimated using the method of Kaplan-Meier.

16.324 Adverse Events: Platelets and hemoglobin will be graded according to the Grading Scale for Hematologic Adverse Events in CLL Studies in Appendix V. The maximum grade for each type of adverse event, regardless of causality, will be recorded and reported for each patient, and frequency tables will be reviewed to determine adverse event patterns. Adverse events will continue to be recorded and reported up to 30 days after the last day of study drug treatment.

16.34 Over Accrual: If more than the target number of patients are accrued, then the additional patients will not be used to evaluate the stopping rule or used in any decision making processes; however, they will be included in final point estimates and confidence intervals.

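### Section 13.5 can stop routine data on treated ineligible patients before the adverse event window closes, and exclusions from the go/no-go count have no deadline or response-blind rule

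*Combined protocol and SAP*

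**What the plan says.** **Data on treated ineligible patients.** Section 13.5 states: "If the patient received treatment, all data up until the point of confirmation of ineligibility must be submitted". Survival follow-up under Section 4.2 then applies. Section 16.324 sets a different end point: "Adverse events will continue to be recorded and reported up to 30 days after the last day of study drug treatment". Section 10.82 asks for all adverse events in exposed subjects from consent to the last study-related procedure, and for serious events to 30 days after the last dose. The stopping rule in Section 16.352 counts treated patients, not evaluable ones.

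**Who counts in the decision.** Sections 16.11 and 16.311 define the evaluable set as eligible, consented patients who have started treatment, "with the exception of patients who are determined to be a major treatment schedule violation". Section 13.7 defines a major violation by Cycle 1 treatment requirements that "are severely violated that evaluability for primary end point is questionable". Section 16.12 sets the numbers: "A maximum of 22 evaluable Cohort 1 and 26 evaluable Cohort 2 patients will be accrued unless undue toxicity is encountered". It adds: "We anticipate accruing an additional 4 patients (2 Cohort 1, 2 Cohort 2) to account for ineligibility, cancellation, major treatment violation, or other reasons". The Cohort 1 rule in Section 16.211 declares the regimen ineffective as follows: "If 2 or fewer successes are observed in the first 22 evaluable patients". Section 16.221 applies the same form to Cohort 2, with 16 or fewer of the first 26.

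**DLBCL.** Under Section 13.8, a patient diagnosed with DLBCL during the first cycle is deemed ineligible, may go on being treated, and is left out of the statistical analysis. The note to Section 11.233 counts DLBCL arising at any time as progression.

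**The concern.** There are two separate problems, and both concern patients who have received study drug.

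First, a site that follows Section 13.5 to the letter may stop sending routine forms once ineligibility is confirmed, even if the patient is still inside the adverse event window or still being dosed. The toxicity summary and any all-treated analysis would then be incomplete for those patients.

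Second, each cohort's only efficacy decision is a count of responders among the first 22 or 26 evaluable patients. Whether a patient is evaluable can be settled at any time, including after response is known to the people deciding, and the major-violation test rests on judgement. A patient who is removed gives up the place to the next one. If removals are related to poor response, the decision rule no longer has the error rate stated for it. Section 13.8 is a written instance: an adverse disease event during treatment takes the patient out of the denominator instead of counting against the regimen.

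**Working it through.** **Part (a): the data rules compared.** Let C be the date ineligibility is confirmed and L the date of the last study drug.

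- Under 13.5, required data other than survival end at C.
- Under 16.324, adverse event recording ends at L + 30 days.
- The rules conflict whenever C comes before L + 30 days. If dosing stops on the day of confirmation (L = C), the gap is 30 days. If dosing continues, the gap is longer. Section 13.8 shows that an ineligible patient may continue.
- Response data are at risk only if C precedes the primary-timepoint evaluation. If C comes later, 13.5 already requires that result.
- Sections 10.41, 10.52, 10.6231 and 10.82 keep serious events, deaths, or both reportable to 30 days, with no eligibility exception. The exposed part is therefore routine adverse event data.

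**Part (b): effect on the decision rule.** Inputs from Sections 16.12, 16.21 and 16.22: n = 22, pass at r = 3, null 0.05, alternative 0.20 (Cohort 1); n = 26, r = 17, null 0.50, alternative 0.75 (Cohort 2); two spare patients per cohort; 22 + 26 + 4 = 52.

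*Step 1, reproduce the plan.* The false-positive rate is P(X ≥ r) for X binomial (n, null).

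- Cohort 1: 1 − [0.95^22 + 22(0.05)(0.95^21) + 231(0.05^2)(0.95^20)] = 1 − [0.3235 + 0.3746 + 0.2070] = 0.095 (0.0948 unrounded). Power at 0.20 is 0.8455.
- Cohort 2: P(X ≥ 17 | 26, 0.50) = 0.0843. Power at 0.75 is 0.9091.

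These match the stated 0.09 / 0.85 and 0.08 / 0.91.

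*Step 2, exclusions unrelated to response.* The first 22 or 26 evaluable patients are still independent draws at the same rate, so nothing changes: 0.0948 and 0.0843.

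*Step 3, upper bound.* Suppose k known non-responders are removed and the next k patients take their places. The cohort passes exactly when at least r of the n + k treated patients respond, so the rate is P(X ≥ r | n + k, null). For Cohort 2, with the null at one half, each extra patient adds half the probability of standing at exactly 16: 0.0843 + 0.0396 = 0.1239, then 0.1239 + 0.0486 = 0.1725 (0.172 to three decimals before intermediate rounding).

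| Non-responders replaced | Cohort 1 (≥3) | Cohort 2 (≥17) |
|---|---|---|
| 0 | 0.0948 (n = 22) | 0.0843 (n = 26) |
| 1 | 0.1052 (n = 23) | 0.1239 (n = 27) |
| 2 | 0.1159 (n = 24) | 0.1725 (n = 28) |

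*Step 4, cost of the opposite policy.* If k such patients were held in the first 22 or 26 and counted as non-responders, only n − k patients could respond and the rate becomes P(X ≥ r | n − k).

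| Held as non-responders | Cohort 1 false-positive rate / power | Cohort 2 false-positive rate / power |
|---|---|---|
| 1 | 0.0849 / 0.8213 | 0.0539 / 0.8506 |
| 2 | 0.0755 / 0.7939 | 0.0320 / 0.7662 |

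**The case against.** Several stronger readings are tempting, and the documents do not support them.

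- *That 13.5 ends data submission.* The statement that nothing further is needed is attached only to never-treated ineligible patients and to cancellations (13.6). Treated patients go to survival follow-up, and Section 10 carries its own duties; 10.88 also has all adverse events recorded on the case report form. One can argue that 13.5 only needs a cross-reference. Two conflicting rules for the same patient remain, however. Most events that the 16.352 rule counts should still surface through expedited reporting, so no failure of that rule is shown.
- *That an all-treated check could not be run.* Section 13.7 keeps major violators in active monitoring, so their data continue. For an ineligible patient removed after the result is known, the response predates confirmation and is already due. The gap is confined to ineligibility confirmed before the primary evaluation.
- *That Cycle 1 doses missed for a reaction make a patient a violator.* Sections 7.7, 7.8 and 8.2 provide for interrupted, held and missed doses. Following them is not a violation, and such a patient stays evaluable.
- *That ineligibility can be declared at will.* It depends on facts at registration, eligibility is verified before registration is accepted (6.2), and supporting documents on entry are due within 14 days (18.5). This narrows the route considerably. Section 13.8 is the exception, because it infers ineligibility from an event during treatment.
- *That the error rate is in fact doubled in Cohort 2.* The bound needs both spare places to go to patients chosen for non-response, while the same places must also cover cancellations and other losses.

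Analysing evaluable patients is also a legitimate, prespecified choice. What stands is the missing deadline, the missing requirement to decide without knowledge of response, and the absence of any analysis that would show whether exclusions mattered.

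**Conclusion.** The point holds in two limited parts.

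(a) Section 13.5 conflicts with 16.324 and 10.82 on how long adverse events are collected in treated ineligible patients. At risk are routine adverse event data, and response data where confirmation precedes the primary evaluation.

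(b) Treated patients can leave the go/no-go count and be replaced under a rule with no deadline and no protection from knowledge of response. The false-positive rate lies between 0.095 and 0.116 in Cohort 1 and between 0.084 and 0.172 in Cohort 2. The lower ends assume exclusions unrelated to response; the upper ends assume two replacements per cohort, all known non-responders. The documents give no expected exclusion rate, so the position within these ranges is unknown. In Cohort 1 even the bound adds only about 0.02; Cohort 2 is the more sensitive.

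Sections 13.8 and 11.233 treat first-cycle DLBCL differently. Section 13.8 also gives two windows, one ending with the first cycle of combination treatment and one with the first cycle of treatment. These need to be reconciled.

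**What to change.** 1. **Section 13.5.** For treated patients, require adverse event data through 30 days after the last dose, and any primary-timepoint response evaluation that is done, regardless of eligibility. State that these patients are included in 16.324 and 16.352.
2. **Section 16.312.** Add one supportive estimate per cohort with all treated patients in the denominator, including those excluded under 13.5, 13.7 and 13.8. Count those without a primary-timepoint response as non-responders.
3. **Sections 13.7 and 16.11.** Major violation concerns Cycle 1 conduct only, so its facts are complete when Cycle 1 ends. Require the decision to be dated and documented before the first combination-phase response evaluation, and made without reference to response, including the assessment at the end of Cycle 1. For any ineligibility, record the registration-time criterion that was failed.
4. **Sections 13.8 and 11.233.** Reconcile the handling of first-cycle DLBCL and the two windows in 13.8.

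Patients later proved ineligible should not be forced into the primary test. That would change the prespecified evaluable set and, if one or two counted as non-responders, would lower Cohort 2 power from 0.909 to 0.851 or 0.766.

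The cost is protocol and SAP wording, a few more case report form pages for a handful of patients, and a supportive response rate that may be slightly lower than the primary one. The primary rule, sample size and treatment do not change.
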